2.3 Rationale for dose and regimen selection

EPO treatment is used in MDS patients early after the diagnosis to induce erythroid response and alleviate the symptoms of anemia. At this stage, iron overload is not expected to be high. In addition, the mechanism by which DFX might be efficacious in this setting is related to the depletion of toxic free iron and possibly to the inhibition of NF- κ B in the malignant cells. High doses of DFX are not required to achieve these objectives. Therefore, the dose of DFX DT is established at 10 mg/kg/day and the dose of DFX FCT is established at 7 mg/kg/day.

The current practice for the use of EPO is so variable and differs among countries and even among physicians. Therefore the dose of EPO in this study is chosen based on the guidelines (ASH-ASCO) published by David McCulloch in 2010. According to that, the starting dose in this study is 40,000 units/week. If increase in Hb is < 1 g/dL and total Hb is < 12 g/dL after 4 weeks, the dose should be increased to 60,000 units/week. If increase in Hb is ≥ 1 g/dL and total Hb is < 12 g/dL, patients should continue the current EPO dose. If Hb increase is ≥ 1 g/dL and total Hb is ≥ 12 g/dL, the patients should hold EPO treatment.

Dose change after 12 weeks of study treatment will also be performed according to the EPO guidelines (Appendix 3). If Hb increase is ≥ 1 g/dL and total Hb is < 12 g/dL, patients should continue the current EPO dose. If Hb increase is ≥ 1 g/dL and total Hb is ≥ 12 g/dL, the patients should hold EPO dose (Table 4-1). According to the EPO guidelines, if after 12 weeks of treatment with EPO, Hb increase is < 1 g/dL and total Hb < 12 g/dL, the patient should discontinue EPO as the patient is not responding. In this study, those patients who do not respond to 12-week-EPO treatment will not be discontinued, but they will be switched to the combination for another period of 12 weeks.

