As the EPO guidelines only provide guidance for EPO use: EPO dosing, dose adjustments and dose discontinuation, and do not specify any criteria for the evaluation of erythroid response in MDS patients, in this study, the assessment of the erythroid response at 12 weeks is performed based on the IWG-2006 criteria ([Appendix 2](#)), which is more widely recognized and used to assess hematologic improvement in anemic patients. An increase in Hb of 1.5 g/dL or more is required for a response. For the assessment of erythroid response, only the hemoglobin component is used and not the reduction of RBC transfusions. As the study population in this trial consists only of patients with low- and Int-1-risk MDS, which receive only few or no transfusions, these patients would otherwise wrongly counted as responders.

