Patients will commence study treatment with EPO at 40,000 units once weekly. EPO will be provided as available in the respective country. The EPO must be self-administered via the subcutaneous route by the patient or competent personal. The patient will be instructed by the investigator to take the study drug as prescribed. All doses planned and prescribed to the patient and all dose changes including reasons for change during the study must be recorded in the eCRF.

During the regular study visits the investigator or pharmacist will administer to the patient an appropriate number of vials or prefilled syringes, respectively, depending on the local availability. The number of vials or prefilled syringes of each strength dispensed will be recorded in the Study Drug Dosing Log. All EPO medication (used and unused) returned by the patient will be counted and the sum entered in the study drug dosing log by the investigator or pharmacist at the study site.

The initial dose is 40,000 units given subcutaneously once a week. If increase in Hb is < 1 g/dL and total Hb is < 12 g/dL after 4 weeks, the dose will be increased to 60,000 units/week. If increase in Hb is ≥ 1 g/dL and total Hb is < 12 g/dL, patients will continue the current EPO dose. If Hb increase is ≥ 1 g/dL and total Hb is ≥ 12 g/dL, the patients will hold EPO dose (Table 4-1).

If after 12 weeks of treatment with EPO, Hb increase is < 1 g/dL and total Hb < 12 g/dL, the patient will discontinue EPO as the patient is not responding. These patients who do not respond to 12-week-EPO treatment will be switched to the combination for another period of 12 weeks. If Hb increase is ≥ 1 g/dL and total Hb is < 12 g/dL, patients will continue the current EPO dose. If Hb increase is ≥ 1 g/dL and total Hb is ≥ 12 g/dL, the patients will hold EPO dose (Table 4-1).

Instruction how to self-administer subcutaneous injections should be provided by the study personal.

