2.2 Data included in the analyses

Data will be collected on patients aged ≥ 18 years or older with low- and-int-1-risk MDS, randomized in 1:1 ratio to DFX+EPO or EPO alone. If after 12 weeks of treatment with EPO alone, Hb increase is < 1 g/dL and total Hb is < 12 g/dL, the patient will switch to combination therapy of EPO and DFX. The study treatment duration is 24 weeks.

As per the current protocol, no interim analysis is planned. All interim (if required) and final CSRs will have a documented medical review by [REDACTED].

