2.9.1.2 Statistical hypothesis, model, and method of analysis

A patient is defined as an erythroid responder if the criterion of Hb increase from baseline ≥ 1.5 g/dL is met at any time within the first 12 weeks period.

Baseline is defined as the last available value within windows of 4 weeks prior to or on treatment start date. No imputation will be performed for missing Hb value.

Difference in proportions between treatment groups with its 95% Agresti-Caffo (Agresti-Caffo 2000) confidence interval will be provided. Erythroid response proportion will be also summarized by treatment group with its 95% Clopper-Pearson confidence intervals (Clopper and Pearson 1934). Analysis will be performed on FAS.

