	Pre-treatment conditions	Post-baseline	Response
Hematological response: If a patient fulfills at least erythroid or platelet or neutrophil response as well as it's corresponding pre-treatment condition	Hb < 11 g/dL at baseline	Hb increase from baseline by ≥ 1.5 g/dL	Erythroid response
	Platelet < 100×10^9 /L at baseline	Increase from baseline $\geq 30 \times 10^9$ /L	Platelet response
	Neutrophil < 1.0×10^9 /L at baseline	Increase from baseline > 100% and increase from baseline > 0.5×10^9 /L	Neutrophil response
Hematologic improvement: If a patient fulfills at least hemoglobin or platelet or neutrophil improvement response without it's corresponding pre-treatment condition	Hemoglobin < 11 g/dL at baseline	Increase from baseline by ≥ 1 g/dL	Hemoglobin improvement
	Platelet $\geq 100 \times 10^9$ /L at baseline	Increase from baseline $\geq 30 \times 10^9$ /L	Platelet improvement
	Neutrophil $\geq 1.0 \times 10^9$ /L at baseline	Increase from baseline > 0.5×10^9 /L	Neutrophil improvement

2.9.2.2 To assess the effect of treatment on erythropoiesis within 24 weeks in patients who were non-responder to EPO alone after 12 weeks and switched to DFX+EPO

Patients who are non-responders to erythroid at week 12 in the EPO group will have to switch to combination therapy, if they continue to participate in the study.

Patients meeting the criterion (Hb increase from baseline ≥ 1.5 g/dL) at any time between week 12 and week 24 will be considered as erythroid responders.

Proportion of erythroid responders between week 13 and 24 will be reported along with its 95% Clopper-Pearson confidence interval. Descriptive statistics will be provided for erythroid response. Analysis will be performed on FAS.

2.9.2.3 To assess the effect of treatment with EPO alone on erythropoiesis within 24 weeks of treatment

This analysis includes patients who started with the EPO alone and are not switched to combination therapy.

Patients meeting the criterion (Hb increase from baseline ≥ 1.5 g/dL) at any time between week 1 and week 24 will be considered as erythroid responders. Proportion of erythroid responders who starts with EPO alone and are not switched to combination therapy will be reported along with its 95% Clopper-Pearson confidence interval.

Descriptive statistics will be provided for erythroid response. Analysis will be performed on FAS.

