2.9.2.4 To assess iron parameters in patients randomized to EPO alone, DFX+EPO and in patients randomized to EPO alone and switched to DFX+EPO after 12 weeks

This analysis will include patients randomized either to EPO or DFX+EPO at baseline as well as patients who are non-responders to erythroid at week 12 in the EPO group switched to combination therapy. The time-course of serum ferritin and its absolute/relative changes from baseline will be summarized by descriptive statistics by visit and erythroid response. Data will be summarized on FAS.

Note: Patients randomized to EPO and not switching after 12 weeks to EPO+DFX, will consist of only responders.

2.9.2.5 To assess Hb parameters in patients randomized to EPO alone, DFX+EPO and in patients randomized to EPO alone and switched to DFX+EPO after 12 weeks

This analysis will include patients randomized either to EPO or DFX+EPO at baseline as well as patients who are non-responders to erythroid at week 12 in the EPO group switched to combination therapy. The time-course of Hb and its absolute/relative changes from baseline will be summarized by descriptive statistics by visit and erythroid response. Data will be summarized on FAS.

Note: Patients randomized to EPO and not switching after 12 weeks to EPO+DFX, will consist of only responders.

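### EPO patients who do not switch are not all responders, and the SAP's crossover text admits patients whom Protocol Table 3-1 excludes

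*SAP*

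**What the plan says.** - **Switch rule.** SAP 2.2: "If after 12 weeks of treatment with EPO alone, Hb increase is < 1 g/dL and total Hb is < 12 g/dL", the patient moves to the combination. Protocol 4.1, Table 4-1 and 6.1.4 and SAP Table 2-1 agree. With a rise of 1 g/dL or more the patient does not switch.
- **Response.** SAP 2.9.1.2: "A patient is defined as an erythroid responder if the criterion of Hb increase from baseline ≥ 1.5 g/dL is met at any time" in the first 12 weeks. Protocol 10.4.2 gives the same definition, and Protocol 2.3 says: "An increase in Hb of 1.5 g/dL or more is required for a response".
- **Label for non-switchers.** SAP 2.9.2.4 and 2.9.2.5, repeated in Protocol 10.5.9 and 10.5.10: "Note: Patients randomized to EPO and not switching after 12 weeks to EPO+DFX, will consist of only responders". The tables it belongs to are split by visit and erythroid response.
- **Label for switchers.** The heading of SAP 2.9.2.2 concerns the effect "in patients who were non-responder to EPO alone after 12 weeks and switched to DFX+EPO". Its body says that patients who are "non-responders to erythroid at week 12 in the EPO group will have to switch to combination therapy, if they continue". Protocol 10.5.2 reads the same way. Protocol Table 3-1 defines this endpoint by two conditions together: no response to EPO alone within 12 weeks, and a switch.
- **Non-switchers again.** SAP 2.9.2.3 estimates the proportion of erythroid responders among EPO patients who did not switch, with a Clopper-Pearson interval.

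**The concern.** The switch rule and the response definition differ in threshold (1.0 against 1.5 g/dL) and in timing (the week-12 value against any value in weeks 1-12). Yet the text uses responder and non-responder as if the two rules divided the EPO arm in the same way.

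Two things are at stake. If the note is followed, EPO-alone patients who never responded are presented as responders in the ferritin and Hb summaries. And Protocol 2.2 gives the crossover analysis the task of showing whether adding DFX works in patients who have already failed to respond to EPO. If its denominator is taken from the body of SAP 2.9.2.2, it can include patients who had responded to EPO.

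**Working it through.** The plan gives no figure to reproduce here. The core check is a cross-classification and needs no assumption.

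**1. Four cells.** Let M be the largest Hb rise in weeks 1-12 and W the week-12 rise. Switched means W < 1.0 with Hb < 12. Responder means M >= 1.5. For a baseline below 10.5 g/dL (the screening limit with the 5% tolerance), W < 1.0 gives Hb below 10.5 + 1.0 = 11.5, so the Hb < 12 clause never changes the result.

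| | Responder | Not a responder |
|---|---|---|
| Not switched | M >= 1.5, W >= 1.0 | 1.0 <= W and M < 1.5 (the gap) |
| Switched | M >= 1.5, W < 1.0 | M < 1.5, W < 1.0 |

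All four cells can occur.
- Gap example: +1.2 at week 12 and never higher. The patient stays on EPO and is not a responder.
- Switched responder: +1.6 at week 8 and +0.8 at week 12. The fall is 1.6 - 0.8 = 0.8, below the 1.5 g/dL discontinuation limit in Protocol 6.1.4, so the patient stays on study and switches.

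The FAS is all randomized patients. Those who leave before week 12, and those wrongly not switched (deviation S06), are also non-switchers who need not be responders.

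**2. Check against SAP 2.9.2.3.** A week 1-12 responder is also a week 1-24 responder. If the note were true, the proportion in 2.9.2.3 would be 100% by construction and its interval pointless.

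**3. Worked example.** Take 30 EPO patients with no dropout and 12 responders (the 40% reference rate in Protocol 10.8). Assume 3 gap patients and 1 responder back below +1.0 at week 12.
- Not switched: 11 + 3 = 14, of whom 3/14 = 21% are not responders.
- Switched: (18 - 3) + 1 = 16, of whom 1 had already responded.
- If 3 of the 15 first-time patients later reach 1.5 g/dL, the Table 3-1 rate is 3/15 = 20.0% (Clopper-Pearson 95% CI 4.3-48.1).
- With the earlier responder counted again it is 4/16 = 25.0% (7.3-52.4). With that patient in the denominator only it is 3/16 = 18.8% (4.0-45.6).

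**4. How many patients.** The documents give no SD for Hb change, so every count below is illustrative.
- Week-12-only normal model with 40% response: mean = 1.5 - 0.253 x SD, and gap share = 0.60 - P(W < 1.0). SD 1.0: 0.60 - 0.403 = 0.197, or 5.9 of 30. SD 2.0: 0.60 - 0.501 = 0.099, or 3.0 of 30.
- Simulation over 60 settings (SD 0.8-2.0, visit SD 0.3 or 0.5, response 20-40%, linear rise or plateau from week 8, discontinuation rule applied): gap median 3.3 of 30 (range 1.3-7.1); earlier responders who switch, median 0.3 (0.0-1.7). Leaving the latter in raises the switch-analysis rate by a median of 0.8 points (0.0-4.1).
- A cruder four-visit model without the discontinuation rule (40% response, SD 1.0 or 1.5, within-patient correlation 0.6-0.9) gave 2.0 to 4.8 gap patients and 0.2 to 3.0 earlier responders who switch; the highest of these needed the weakest correlation.
- If response is judged to week 24, visit noise alone carries about 40% (28-53%) of gap patients over 1.5 g/dL. In a similar assumed model this left 1.9 of 30 (0.7-3.8), down from 3.2.

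**The case against.** **The note may use responder in the EPO-guideline sense.** Protocol 2.3 says "In this study, those patients who do not respond to 12-week-EPO treatment will not be discontinued, but they will be switched to the combination" and Protocol 6.1.1 says "These patients who do not respond to 12-week-EPO treatment will be switched to the combination for another period of 12 weeks", both for a rise below 1 g/dL. In that sense the note would hold for patients correctly assessed at week 12. But it belongs to tables split by erythroid response, and Protocol 2.3 sets 1.5 g/dL for a response. SAP Table 2-2 classes a rise of 1 g/dL or more as hemoglobin improvement, apart from erythroid response. This defence fails.

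**A reader might infer that the label for switchers is false too.** It is not. Every switcher has a week-12 rise below 1.0, hence below 1.5, so non-responder at week 12 is literally true at that visit.

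**A reader might infer that the plan deliberately puts earlier responders in the crossover analysis.** The documents do not support that. Table 3-1 excludes them, and the 2.9.2.2 heading also joins the two conditions. What stands is a mismatch between the body text and Table 3-1. It involves few patients, and the three intervals in the example overlap almost completely.

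**A reader might infer that measuring post-switch response from the pre-EPO baseline is an error.** That baseline is prespecified. Restarting from Hb at switch brings regression to the mean, because patients were selected for a low value. It gave no reduction in 6 of the 60 settings, and it still does not separate DFX from continued EPO. Either baseline is defensible if the limit is stated.

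**The ferritin and Hb tables do not depend on the note.** This stands: their split by erythroid response already yields the right rows if a non-responder row is kept for the not-switched group.

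**Conclusion.** The point holds, for secondary and descriptive analyses only. The note is false under the plan's own definitions, whatever the SDs. The 2.9.2.2 body text (and Protocol 10.5.2) disagrees with Table 3-1 about an early responder who has slipped below +1.0 at week 12. That patient could count as an EPO responder in the primary analysis and again after the switch.

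The size is modest and rests on assumed SDs: roughly 1 to 7 of 30 EPO patients in the gap at week 12, fewer if response is judged to week 24, and usually under 1 of 30 earlier responders who switch. The gap is the larger problem. It would go too far to infer that the primary comparison is affected, since it uses the 1.5 g/dL definition within 12 weeks in the arms as randomized. I take no view on the clinical switch rule.

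**What to change.** A SAP correction is enough. Protocol 12.1 requires a written, approved amendment for any protocol change, so the matching protocol text can wait for an amendment made for other reasons.

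1. Delete the note in SAP 2.9.2.4 and 2.9.2.5. Label the EPO groups switched and not switched. Keep the split by the 1.5 g/dL erythroid response, with a non-responder row in the not-switched group, and state whether response is judged to week 12 or week 24.
2. In SAP 2.9.2.2, align the denominator with Protocol Table 3-1: EPO patients who switched and had not met 1.5 g/dL before the first DFX dose. List switchers who had already responded separately, outside numerator and denominator.
3. Keep the pre-EPO baseline for the post-switch endpoint. State that the rate includes any rise gained on EPO alone (up to almost 1 g/dL at week 12) and does not separate DFX from continued EPO. A descriptive result from Hb at switch is optional and would need a regression-to-the-mean caveat.

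The cost is minor rewording and one flag from Hb data already collected. The clinical switch rule and the planned endpoint stay as they are.

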To estimate duration of erythroid response among responders treated with EPO alone	Duration of erythroid response is defined as the time from onset of the first response to progression/relapse (decrease in Hb \geq 1.5 g/dL from Hb value at response) among responders treated with EPO alone within the whole 24 weeks period	Refer to Section 10.5.7

Objective	Endpoint	Analysis
To estimate duration of erythroid response among responders treated with DFX+EPO	Duration of erythroid response is defined as the time from onset of the first response to progression/relapse (decrease in Hb \geq 1.5 g/dL from Hb value at response) among patients randomized to EPO+DFX up to week 24 and for patients switched from EPO to DFX+EPO from week 13 to week 24	Refer to Section 10.5.8
To evaluate tolerability and safety of the combination	Incidence of adverse events (AEs) overall and by severity, and serious adverse events (SAEs).	Refer to Section 10.5.11
To assess iron parameters in patients randomized to EPO alone, DFX+EPO and in patients randomized to EPO alone and switched to DFX+EPO after 12 weeks	Change in SF from baseline to every visit in patients throughout in the combination arm, throughout in the EPO arm and switched from EPO arm to EPO+DFX after 12 weeks	Refer to Section 10.5.9
To assess Hb parameters in patients randomized to EPO alone, DFX+EPO and in patients randomized to EPO alone and switched to DFX+EPO after 12 weeks	Change in Hb from baseline to every visit in patients throughout in the combination arm, throughout in the EPO arm and switched from EPO arm to DFX+EPO after 12 weeks	Refer to Section 10.5.10
Supportive		
To assess the effect of treatment with DFX+EPO and EPO alone on hematologic improvement within 24 weeks of treatment	Proportion of patients achieving a hematologic improvement (improvement of neutropenia and thrombocytopenia) within 24 weeks of treatment with DFX+EPO and EPO alone	Refer to Section 10.5.1
To assess the effect of treatment with DFX+EPO and EPO alone on total hematological response within 24 weeks of treatment	Proportion of patients achieving a hematological response (increase in Hb, improvement of neutropenia and thrombocytopenia) according to modified IWG 2006 criteria and patients achieving a hematologic improvement (improvement of neutropenia and thrombocytopenia) within 24 weeks of treatment with DFX+EPO and EPO alone	Refer to Section 10.5.1

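### No between-arm estimate is specified for Hb or serum ferritin change over weeks 1-12, and the planned display divides the EPO arm by its own week-12 Hb result

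*SAP*

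**What the plan says.** Protocol Table 3-1 defines both continuous endpoints by three groups. The Hb entry reads: "Change in Hb from baseline to every visit in patients throughout in the combination arm, throughout in the EPO arm and switched from EPO arm". The ferritin entry has the same form: "Change in SF from baseline to every visit in patients throughout in the combination arm, throughout in the EPO arm and switched from EPO arm". In both, the switch is to the combination and follows week 12.

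The planned analysis is descriptive. SAP 2.9.2.5 gives, for Hb: "The time-course of Hb and its absolute/relative changes from baseline will be summarized by descriptive statistics by visit and erythroid response". SAP 2.9.2.4 gives, for ferritin: "The time-course of serum ferritin and its absolute/relative changes from baseline will be summarized by descriptive statistics by visit and erythroid response". Both sections use the FAS and carry the note: "Patients randomized to EPO and not switching after 12 weeks to EPO+DFX, will consist of only responders". Protocol 10.5.9 and 10.5.10 match, with the PP set added.

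The rule that separates the two EPO groups is in SAP 2.2, which moves a patient to the combination on this condition: "If after 12 weeks of treatment with EPO alone, Hb increase is < 1 g/dL and total Hb is < 12 g/dL". Under Protocol 4.1 the same Hb result in the combination arm leads to discontinuation from the study.

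The only between-arm efficacy contrast with a confidence interval is the difference in week-12 erythroid response (SAP 2.9.1.2).

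**The concern.** Group membership in the EPO arm is known only at week 12, yet change is tabulated from baseline at every visit. The earlier values in the two EPO groups are therefore selected on a later outcome. For Hb, the selecting variable is the one being summarised. The further split by erythroid response, defined as an Hb rise of at least 1.5 g/dL, conditions on it again.

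A small pilot of a chelator added to EPO should show whether Hb and ferritin moved differently between the randomised arms while both were still on assigned treatment. After week 12, EPO patients with a poor Hb rise cross over and combination patients with the same result leave, so later visits cannot answer that. If the three-group table is the only display for weeks 1-12, the reader sees the combination arm beside an EPO group chosen for having done well and another chosen for having done badly.

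**Working it through.** **No figure of the plan's own to reproduce.** Neither document gives a mean, SD or expected difference for Hb or ferritin change. The only design figures (Protocol 10.8, SAP 2.11) are intervals for the binary response difference. Nothing below uses them.

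**What is planned for weeks 1-12, by arm as randomised**
- SAP 2.9.1.2: binary response, difference with 95% CI. Not a continuous outcome.
- SAP 2.9.2.4-2.9.2.5: descriptive statistics; no difference and no CI.
- SAP 2.10.3: Hb box plots at each visit (a display, not an estimate). Change to worst value and to end of treatment, for Hb and ferritin, is not limited to weeks 1-12 and can include post-switch data.
- Protocol 10.5.11.3: observed values and changes for haematology and iron parameters; neither visit nor arm is named, and no contrast.

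**The effective cut-point.** Screening Hb is below 10 g/dL, or up to 5% above that (10.5 g/dL) at the investigator's discretion. A rise below 1 g/dL then leaves Hb below 10.5 + 1 = 11.5 g/dL, so the second condition (Hb below 12 g/dL) is met automatically if baseline is in this range. The split is in effect at a rise of 1.0 g/dL.

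**Illustration for Hb (assumed values).** Let week-12 change be normal with mean m and SD s in both arms, so deferasirox has no effect. With a = (1.0 - m)/s, φ and Φ the standard normal density and distribution function:

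- mean of EPO non-switchers = m + s·φ(a)/(1 - Φ(a))
- mean of EPO switchers = m - s·φ(a)/Φ(a)
- non-switchers minus combination arm = s·φ(a)/(1 - Φ(a))

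| m | s | a | Non-switchers minus combination (g/dL) |
|---|---|---|---|
| 1.0 | 1.3 | 0 | 1.3 × 0.399/0.500 = 1.04 |
| 1.4 | 1.0 | -0.40 | 1.0 × 0.368/0.655 = 0.56 |
| 0.6 | 1.6 | 0.25 | 1.6 × 0.387/0.401 = 1.54 |

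The last two rows are the extremes over m from 0.6 to 1.4 and s from 1.0 to 1.6. In the first row non-switchers average +2.04 and switchers -0.04, against +1.00 in the combination arm.

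**With a real effect.** A simulation with a true benefit of 0.5 g/dL (EPO mean 0.8-1.1, SD 1.0-1.5, also assumed) gave combination minus non-switchers of -0.24 to -0.83 g/dL, the wrong sign. Combination minus switchers was +1.18 to +1.76. The all-randomised contrast returned 0.50.

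**Pooling.** In the first row half the EPO arm is in each group: 0.5 × 2.04 + 0.5 × (-0.04) = 1.00, the full-arm mean. So the information is not destroyed, provided every EPO patient is in one of the two groups.

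**Precision of the missing estimate.** With 30 per arm and no baseline adjustment, the 95% half-width for a difference in means is 1.96 × s × √(2/30) = 0.506s. For assumed s of 1.0, 1.5 and 2.0 g/dL this is 0.51, 0.76 and 1.01 g/dL.

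**Data available (Protocol Table 7-1).** After randomisation and up to Visit 10 (nominal Day 84, SAP Table 4-1), haematology is drawn at Visits 5, 7, 9 and 10, and at Visit 8 only if EPO was increased at Visit 7. Serum ferritin is drawn at Visits 7, 9 and 10.

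**The case against.** The strongest reply is that the three-group reading is not forced. SAP 2.9.2 opens by saying secondary endpoints are analysed by treatment arm. Sections 2.9.2.4-2.9.2.5 cover patients randomised to either arm as well as switchers, on the FAS, which follows assigned treatment. Where the SAP wants switchers left out, as in 2.9.2.1 and 2.9.2.3, it says so. A full EPO column plus a switcher subset is therefore possible, and the table shells (RAP Module 7) are not available to settle it. This stands in part: the general phrases leave that reading open. They do not clearly override Table 3-1, though, and the note on non-switchers treats them as a group of their own. On either reading no difference or CI is specified.

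Second, a reader might infer that weeks 1-12 yield no between-arm information at all. That goes too far. Means and SDs for the two EPO groups could be pooled, Hb box plots by visit are planned, and the primary analysis compares the randomised arms on an Hb-based response. But pooling is not planned, does not work for medians, and fails for EPO patients who leave before week 12, to whom Table 3-1's wording gives no group.

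Third, a reader might infer that the trial will report a spurious deficit of about 1 g/dL for deferasirox. The documents do not support that. The figure rests on assumed values and on a contrast that the SAP does not formally plan. Nor does it transfer to ferritin, which is not the selecting variable and for which nothing has been quantified.

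Finally, a descriptive pilot with no formal sample size calculation need not test secondary outcomes. That is right, but an estimate with an interval is not a test.

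**Conclusion.** The point holds as a gap in specification. Protocol Table 3-1 and SAP 2.9.2.4-2.9.2.5 present Hb and ferritin change with the EPO arm divided by its week-12 Hb rise and again by erythroid response, and no between-arm difference with a CI is specified for weeks 1-12. The illustrative Hb gap of 0.56-1.54 g/dL shows how far outcome-selected columns could mislead an informal comparison. It assumes normal changes, no deferasirox effect, and means and SDs that the documents do not give.

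It would also be tempting to say that discontinuing combination patients at week 12 hides any true effect. The documents do not say those patients are dropped from the FAS tables. Even if only patients with a rise of at least 1 g/dL were compared in both arms, the simulated 0.5 g/dL effect shrank to about 0.2 rather than vanishing.

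The primary analysis is unaffected. This is an inexpensive improvement, not a flaw in the main result.

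**What to change.** In SAP 2.9.2.4-2.9.2.5 and Protocol 10.5.9-10.5.10:

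- Add an FAS analysis by randomised arm up to Visit 10, before any switch: ANCOVA at Visit 10, or a repeated-measures model, with the baseline value as covariate. Use Hb at Visits 5, 7, 9 and 10, and log serum ferritin at Visits 7, 9 and 10. Leave out Visit 8, because whether it takes place depends on a poor week-4 Hb rise. Report the arm difference with its 95% CI as an estimate, not a test.
- Use the three-group display for visits after Visit 10 and label it non-randomised.
- Switchers' ferritin change may also be shown from Visit 10, since change from the original baseline mixes 12 weeks of EPO alone with the combination period. If Hb change from Visit 10 is shown, state that it is subject to regression to the mean, because that Hb value is what selected these patients.
- Label any Hb table split by response as descriptive only.

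Cost: SAP and protocol wording, plus one model and one table per variable, with no new data collection. Stopping EPO at Hb of 12 g/dL or more may reduce the mean Hb difference; the amount has not been calculated.
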